5.5 Secondary Outcome Measure

1. Point of delivery outcomes:
 - Acceptability of targeted HIV SSK distribution, including rationales for accepting or refusing the offer of an SSK
 - Acceptability and feasibility of targeted SSK distribution among specified service providers, including utility of protocols for SSK targeting, offers and intervention uptake.
2. Data collection outcomes:
 - Demonstration that intervention models and service provider training and support incorporates sufficient capacity to successfully record the numbers of: people offered SSK, accepting SSK, and returning SSK
 - Feasibility of collecting correct contact details enabling follow-up, reminders and communication of results
3. Pathway to care outcome measures:
 - Proportion of those whose samples are reactive who: a) are informed of results in person and b) who attend for confirmatory testing at an NHS setting of their choice
4. Overarching outcome measures:
 - Cost per person kit distributed and cost per HIV diagnosis per setting
 - Attrition rates and loss to follow up
 - Confirmatory testing, proportion of those receiving an HIV positive diagnoses, and clinical stage at diagnosis
 - Feasibility and sensitivity of outcome measures (testing, behavioural and economic) for a definitive trial.

6. Study Design

This is a prospective, mixed-methods, non-randomised study. The study evaluates the effectiveness of self-sampling for HIV as well as the cost effectiveness of distributing the SSK through GP settings and Community based organisations. Feasibility and acceptability will also be assessed through a process evaluation. Please see the fieldwork schematic diagram in section 6.1 for further information.

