6.3 Study Eligibility

6.3.1 Inclusion Criteria

To be recruited into the study, participants will need to be:

- Black African
- Without diagnosed HIV,
- 18 years of age or older
- Accessing GP practices or community based organisations that are taking part in the study.
- Able to provide informed consent.
- Able to read and understand English.

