6.6 Screening Procedures

6.6.1 GP Practices

Practice nurses will go through their patient list each morning and identify patients scheduled to visit in each session who are potentially eligible to participate in the study. The eligibility criteria indicated in section 6.3.1 will inform the screening process. The details of potential participants will be entered onto the screening and enrolment log (appendix 3). Only patients on the screening log will be offered the opportunity to take part in the study. Data on patients who are known not to meet the eligibility criteria will not be collected. Reimbursement for the time taken to screen for potential participants will be met through CRN research support costs (NIHR CRN in London and the Scottish Primary Care Research Network in Glasgow).

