6.6.2 Community Based Organisations

The eligibility criteria indicated in section 6.3.1 will be used to identify potential participants during routine outreach and the provision of other services by trained CBO workers. The details of these potential participants will be entered onto the screening and enrolment log (appendix 3). Reimbursement for the time taken to screen for potential participants will be met from the study budget.

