6.7.2 Targeting and Recruiting

The distributor will aim to introduce and recruit eligible candidates to the research study. They will explain the benefits of participating and having an HIV. All distributors will answer questions and aim to alleviate any concerns participants may have. The script below initiates the recruitment process:

“We are currently involved in an important study that I wonder if you’d be interested in taking part in? We want to see if people will use HIV self-sampling kits. HIV treatments are so good now; that you can live a normal healthy life with HIV, and being on treatment also stops most people from passing on the infection. So we are trying to find new ways to offer testing as it’s the people who don’t know their HIV status who become unwell.

This study is looking at whether people from the Black African community would want to use these kits. It’s a great opportunity as most people don’t have access to them yet.

Testing is very easy. It's all in this kit, which you take home to use when it is convenient to you. Once you've collected the sample you put it in the envelope provided and pop it in the post.

A few days later you are contacted by a NHS health clinic via your mobile phone with the results. Most people testing will be negative. A few people will have a test suggesting they have HIV (this is called a 'reactive' test) and we would have to check the result is correct.

It's all completely private and confidential - no one, other than the clinic contacting you, will know your result unless you want them to. What do you think? Is this something that you may be willing to try?"

If answer = NO then go to section A

If answer = YES then go to section B

Section A

"That's absolutely fine. We would really like to understand why people do not want to participate in the study. On this card are some of the common reasons why people say no – "

(Hand participant card)

"Would you possibly be able to let me know if any of the numbers match with your own reason? And if so which numbers? Of course it is also ok if you do not want to give me a reason."

(Participant gives reason or declines to do so)

(If reason given then insert into participant screening and enrolment log)

(Contact ends)

Section B

"First we need to determine if you're eligible for the study. Are you aged 18 or older and do you consider yourself Black African?"

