Appendix 3 HAUS Study Participant Screening and Enrolment Log

Name of Person Screening and Enroling participants										
Site name and Address										
ID Number	Sex		Initials	Age (years)	Country of Birth	Screening Date (dd/mm/yy)	Enrolled?		Reason if not enrolled (insert number from list below) If Did Not Attend insert #11	Comments
	M	F					 Yes	 No		
							 Yes	 No		
							 Yes	 No		
							 Yes	 No		
							 Yes	 No		
							 Yes	 No		
							 Yes	 No		
							 Yes	 No		
							 Yes	 No		
							 Yes	 No		
							 Yes	 No		
							 Yes	 No		
							 Yes	 No		
1. Recently tested for HIV 2. Do not believe at risk of HIV 3. Prefer to test elsewhere 4. Prefer not to use a self-sampling kit 5. Prefer not to know HIV status 6. Do not like being offered an HIV test just because black African 7. Already knows is HIV positive 8. Prefer not to say 9. Other 10. Does not meet eligibility criteria 11. Did not attend										

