Appendix 4: Baseline Questionnaire

Thank you for agreeing to be part of this study. Please complete the following information. The questionnaire is confidential and takes less than 5 minutes to fill in.

First Name _____

Surname _____

Affix Kit
number here

Are you: Male Female

What is your date of birth: //

Mobile number: What is the first half of your
postcode:

Alternative contact method (landline):

1. When did you last have an HIV test? (please tick one)

- Never
- Less than one year ago
- 1 – 2 years ago
- 2 – 5 years ago
- More than 5 years ago

2. In the last 12 months, who have you had sex with

- I have only had sex with men

- I have only had sex with women
- I have had sex with men and women
- I have not had any sex

3. In what country were you born?

Please write it down:

4. How long have you been living in the UK?

- Less than one year
- 1 – 2 years
- 2 – 5 years
- 5-10 years
- More than 10 years
- All my life

Once finished please return this to the person who is enrolling you in the Haus study.

Thank you.

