Appendix 9: Pathway to care outcome measures

1. SSK number	
2. Patient initials	
3. Patient DOB	DD/MM/YYYY

If sample indeterminate:

How was the participant informed of the result:

- . Phone
- . SMS
- . Other _____
- . Not informed of result – reason _____

Outcome:

Attended alternative site for HIV testing Yes No Don't know
Additional SSK sent Yes No SSK number:

If sample reactive:

How was the participant informed of the result:

- . Phone
- . SMS
- . Other _____
- . Not informed of result – reason _____

Did the Participant attend for confirmatory testing? Yes No Don't know
If yes when and where: _____

If no why not if known: _____

What was the confirmatory result: HIV positive HIV negative

If HIV positive, first CD4 count : _____

Appendix 10

Haus Study Researcher Diary

These diaries will remain entirely confidential within the core research team. In the main, these will be analysed by [name] and [name] for the purposes of the process evaluation, but also be aware that they can be accessed by any member of the core team. We plan to monitor these entries monthly, and all core team members are asked to submit **AT LEAST ONE DIARY ENTRY PER MONTH starting from February 2016.**

1. **Researcher Initials:**
2. **Date:**
3. **Was there a particular issue that stimulated the entry? Or is this a routine entry?**
4. **What thoughts / reflections / successes / challenges would you like to record in this entry?**
5. **Is there someone inside / outside of the team that you should speak with about these issues, either for the immediate benefit of the study (in terms of problem-solving) or for you to gain support?**

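### The scripted eligibility check omits known HIV status and the pathway form cannot separate new from prior diagnoses, which exposes cost per diagnosis and related secondary outcomes, mainly in the community setting

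*Protocol*

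**What the plan says.** The inclusion criteria (6.3.1, repeated in section 3.3 of the intervention manual) require participants to be "Without diagnosed HIV".

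Script Section B in 6.7.2 is introduced as the step that determines eligibility. Its only question is "Are you aged 18 or older and do you consider yourself Black African". A yes leads directly to Section B2, headed as eligible, and to the information sheet and consent form.

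Screening comes before the script. For GP practices (6.6.1), nurses go through the day's patient list and "The eligibility criteria indicated in section 6.3.1 will inform the screening process". For community organisations (6.6.2), the same criteria "will be used to identify potential participants during routine outreach and the provision of other services by trained CBO workers"; no source of information on HIV status is given.

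The remaining instruments:
- The baseline questionnaire (Appendix 4) asks when the last HIV test was, not its result.
- The consent items listed in 6.7.3 and the sample data form (Appendix 7) have nothing on known status.
- The screening log (Appendix 3) has a code "Already knows is HIV positive", but as a reason for non-enrolment.
- For a reactive sample, the pathway form (headed Appendix 9, cited in 6.10 as appendix 10) asks whether the participant attended confirmatory testing, with free text for why not, then "What was the confirmatory result: HIV positive HIV negative" and the first CD4 count.

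Secondary outcomes in 5.5 include "Cost per person kit distributed and cost per HIV diagnosis per setting", the proportion diagnosed positive and clinical stage at diagnosis.

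**The concern.** The script contradicts the criterion it is meant to apply. A person with diagnosed HIV who answers truthfully is told that they are eligible. The other criteria have some check in the process: date of birth and contact number on the baseline form, reading the study papers, signing consent. Known HIV status has none that the document names once the script begins.

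If such a person returns a kit and attends for confirmation, the form shows a confirmed positive and a CD4 count. Nothing marks the diagnosis as old. The person then enters the proportion diagnosed, clinical stage at diagnosis (although that CD4 count need not date from diagnosis), linkage to care, and the denominator of cost per diagnosis. The last of these feeds the budget impact analysis in 7.2.3. The safeguard also differs between GP and community recruitment, so the error would fall unevenly across the settings that are to be reported side by side. An analysis plan cannot repair this later, because no form holds the information.

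**Working it through.** **The protocol's own figure.** It states no expected number of diagnoses. Its stated precision for the return rate (7.1) reproduces as a two-sided 95% half-width (level assumed): 1.96 × √(0.25/600) = 4.00% and 1.96 × √(0.25/380) = 5.03%, against ±4.0% and ±5.0%. The kit numbers and the 50% return rate are therefore used as given.

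**Inputs.**
- Kits: 600 London GP, 600 London community, 380 Glasgow GP (Study Summary).
- Return rate: 50% (7.1), giving 300, 300 and 190 returned samples.
- HIV prevalence p: nearly 4 in 100 (manual 1.1) to about 1 in 20 (manual 5.1).
- Share of people with HIV who are unaware: about 1 in 3 (manual 5.1).

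**Expected new diagnoses if 6.3.1 is applied as intended.** The undiagnosed proportion among people without diagnosed HIV is u = (p/3) / (1 − 2p/3).
- p = 4%: 0.01333/0.97333 = 1.37%.
- p = 5%: 0.01667/0.96667 = 1.72%.

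| Setting | Returns | Expected new diagnoses |
|---|---|---|
| Each London setting | 300 | 4.1 to 5.2 |
| Glasgow | 190 | 2.6 to 3.3 |
| All settings | 790 | 10.8 to 13.6 |

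**Effect of one known positive counted as new.** With total cost held fixed, cost per diagnosis falls by 1/(N + 1), where N is the expected number of new diagnoses.
- London: 1/6.17 = 16% to 1/5.11 = 20%.
- Glasgow: 1/4.28 = 23% to 1/3.60 = 28%, though Glasgow recruits only through GP practices, where lists are screened.
- With a 60% return rate, the London expectation is 4.9 to 6.2, and one person lowers the cost by 14 to 17%.

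**Illustration only.** On the manual's figure, diagnosed people outnumber undiagnosed by 2 to 1. If a diagnosed person took and returned a kit at r times the rate of an undiagnosed person, the share of counted diagnoses that are not new is 2r/(1 + 2r): 17% at r = 0.10, 33% at r = 0.25, 50% at r = 0.50. The document gives no value for r.

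**The case against.** Section B is not the only check. GP lists are screened against 6.3.1 first, and only logged patients are offered the study. GP settings hold 600 + 380 = 980 of the 1580 kits (62%). This stands, and it confines the gap mainly to the London community setting.

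A reader might infer that the log code catches only people who volunteer their status. The document does not support that. People who decline are handed a card of numbered reasons, and the log takes a number from a list that includes this one, so the code is probably prompted. It still covers only people who are not enrolled.

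A reader might also infer that Appendix 9 can never show a prior diagnosis. That is too strong: its free-text reason for not attending could record a known positive who tells the health advisor and does not re-test. The person who does re-test is not distinguished.

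The consent form, the information sheet and the manual's own recruitment script are not in the text at hand and may mention HIV status. If they do, fewer known positives would enrol, but those who did would still not be identifiable on Appendix 9 after re-testing.

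Finally, the outcomes are secondary in a feasibility study, and the counts are imprecise in any case: the exact 95% Poisson interval for 4 events is 1.1 to 10.2. That limits the severity. It does not remove the point, because sampling error can be shown with an interval, whereas this error runs in one direction, varies by setting and cannot be seen in the data.

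**Conclusion.** The defect holds and should be fixed, but it does not undermine the study. The script declares eligible a person whom 6.3.1 excludes, and the pathway form cannot separate a new from a prior diagnosis in someone who re-tests. The exposure lies mainly in London community recruitment and in the secondary and economic outcomes. The primary return rate is affected only in so far as ineligible people enter its denominator.

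One such person lowers a London setting's cost per diagnosis by about 16 to 20%. This assumes that the quoted national prevalence and unaware share apply to participants, that half the kits are returned and that total cost is unchanged; no figures by city or setting are given.

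A reader might go further and infer that 17 to 50% of counted diagnoses would not be new. The document does not support that. Those shares rest on assumed uptake ratios and ignore the GP list screening.

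**What to change.** 1. Extend script Section B, and the matching manual script, to confirm every 6.3.1 criterion. A card listing the criteria, with one question on whether all of them apply, avoids anyone having to state their HIV status aloud.
2. Add one item to Appendix 9: HIV diagnosed before this kit, yes / no / not known. The health advisor already phones each participant with a reactive result and contacts HIV services (6.10), so no new contact is needed.
3. State that only new diagnoses count in the proportion positive, stage at diagnosis and cost per diagnosis.

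The cost is a script line with a card, one form item and one counting rule, with no extra staff. The wording needs care because the question is sensitive. The eligibility check would still rest on self-report, so a person who conceals a diagnosis could pass it; the Appendix 9 item is the second line of defence.

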6.7.3 Consent Process

Participants who are eligible and agree to take part in the study will be given either the paper consent form to complete or they can be given study tablets to complete the consent form online.

Participants will consent to the following:

- a) Taking part in the study.
- b) Supplying a telephone number that can be used to contact them.
- c) Receiving reminder messages if their sample is not received at the laboratory (optional).
- d) Contact by NHS provider to provide them with their result.
- e) Notification of their GP of the result (optional) and only in the GP setting.
- f) Additional contact by phone or email for a telephone interview to explore the process and acceptability of self-sampling (optional).
- g) Audio recording of telephone interviews (optional)

The screening log (appendix 3) will also function as an enrolment log. In it, distributors will detail all eligible patients, whether or not they have approached them and if they have agreed to take part or not, and if not the reason for refusal if provided.

Please note it is not our intention to specifically notify the GP when a participant recruited in their practice consents to participate. We are specifically requesting consent to inform the GP of the

HIV test result (be it negative or reactive). If consent is obtained then the GP will be made aware of the result and that participation has occurred. If consent is not obtained or if the sample is not returned to the laboratory for processing then the GP will not be informed. The GP of all those recruited via community based organisations will also not be informed of either participation or test result.

6.7.4 Baseline data

Participants who are successfully recruited into the study should then be asked to self-complete a short baseline questionnaire. The baseline questionnaire (appendix 4) will collect kit specific identification number; name, contact details (mobile or landline number), demographics (age, gender, country of birth) and details about prior HIV testing and sexuality. The baseline questionnaire will be available in electronic and paper based formats. The mode used will depend on provider and user preference and whether internet access is available. If a paper based version is used, the data will need to be subsequently entered directly by the distributor onto the study database via a web link later that day. All study sites will be provided a study tablet by the research team.

6.7.5 Demonstration of the kit

Once they have completed the questionnaire, the distributor will give the participant a self-sampling kit and briefly explain the processes involved with kit use. See intervention manual (appendix 6) for supporting text and suggested script to accompany this process. Additional information on how to use the self-sampling kit, the importance of posting the sample to the laboratory for processing and the use of reminder texts to participants should the sample not be received at the lab will be highlighted in the participant information sheet and kit inserts. They will also explain how results will be communicated to the participants.

6.8 Follow up of participants

6.8.1 Quantitative

As detailed in section 6.5.2 every kit will contain a brief acceptability questionnaire (appendix 5). The questionnaire will explore acceptability of being offered a SSK in that setting, acceptability of targeting and the process of using the kit. Each kit will come with a unique ID number, this number will be entered onto the baseline and acceptability questionnaires as well as the recruitment log, and will allow the research team to link data from the two

questionnaires with that of the test result. These data will give insight into the key features and characteristics of acceptability among those who ultimately have used the kit.

6.8.2 Qualitative

During the recruitment and consenting process participants will be asked to consider taking part in optional follow up telephone interviews (n=30).

The participants will be purposively sampled to ensure a spread of those who:

- Agree to participate but do not return sample (x10)
- Agree to participate and return sample (x20)

Of those 20 that have returned the SSK we seek to interview 10 people recruited in GPs and 10 recruited by CBOs. Ten to fifteen people will be recruited in London and five to ten recruited in Glasgow. This is an ideal sampling frame, and will depend on willingness to interview among participants in each category. Verbal consent to proceed with the interviews at a mutually convenient time will be obtained again when telephone contact is made. Interviews will be undertaken by phone and are anticipated to last up to 30 minutes. Those who take part will be sent a £10 voucher for their time. If consent is obtained interviews will be recorded and fully transcribed. All transcripts will be fully anonymised. Framework analysis will be undertaken with the use of NVivo 10. Interview data will enable assessment of outcomes indicators relating to the facilitative and inhibiting factors involved in participants' decisions to accept and utilise the SSK. Interviews with non-returners will specifically explore reasons for not returning the sample, satisfaction with the intervention; suitability, strengths and weaknesses of the intervention; willingness to use it in the future and suggested improvements.

6.9 Sample Collection and Analysis

Participants will be required to self-collect a sample of blood using the TINY vial in the kit provided to them. As indicated in section 6.5.3, there will be instructions including a video link on how to collect the sample. Participants will also be required to complete the form with three unique identifiers (that is initials, date of birth and unique ID number) to enable the sample to be processed at the laboratory. The ID number will be pre-populated on both the lab form and the acceptability questionnaire.

UCLH will be responsible for the following:

1. UCLH via TDL will process samples as soon as they are received.

2. UCLH-TDL will send a CSV file for the study manager of returned samples to enable the manager to send out two reminder texts to participants whose kits have not been returned. This will be sent as an encrypted email.
3. UCLH-TDL will send a CSV file with results for each of the samples returned so that these results can be entered on the database by the study team. This will be sent as an encrypted email.
4. UCLH-TDL will collect the acceptability questionnaires returned with the sample, store them in a locked cabinet and pass these onto the study team.

[figure not shown]
